#### **Range of imposed performance variations (part B) – Treadmill walking**

A treadmill familiarization procedure will ensure that every participant is enrollable to perform experimental part B. The subjects will be asked about previous experiences with treadmill training/use and this will be noted down in the participant file: participants will undergo 10 minutes of treadmill walking with the supervision of a physiotherapist to familiarize with the moving belt, position and use of safety bars and other general safety and usability issues.

A speed-range definition procedure will permit the quantification of the appropriate personalized range of experimentally-induced performance variations for every participant. All the participants will start walking on the treadmill at 50% of their *maximal treadmill walking speed* (speed calculated from their overground performance in 6MWT: maximal speed maintained for at least 15 seconds during the test) and they will be asked to confirm if that is their *comfortable treadmill walking speed*; if this is not the case the experimenter will adjust the speed based on the participant's subjective reports and, finally, will let them walking at that constant speed for one minute.

Immediately after the selection of their *comfortable treadmill walking speed* (i.e. during the one minute of constant speed walking) the participants will be instructed to maintain their position on the treadmill, in the antero-posterior direction, adapting their gait to the belt continuous acceleration toward their maximal walking speed (selected from their overground performance in 6MWT, see paragraph above). This speed range, will be used as personalized range of experimentally-induced performance variations (in Part B).

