During the experimental perceptive task the imposed speed will vary from the baseline in an upward/downward fashion with fixed increments (of 0,028m/s) but with randomized time in between every acceleration: the increase in speed will continue for 15 consecutive incremental steps, although never trespassing the participant's maximal speed (derived from their overground performance in first minute of 6MWT, see above), it will stabilize on that value before decreasing toward the baseline speed (with the same number of consecutive steps). As demonstrated in the example, in figure 5, this protocol will last 6 minutes and will impose the absolute magnitude of speed changes (0,42 m/s) for all participants and it will be divided in 3 phases: 1 minute of stable comfortable speed, 150 seconds of speed increments and 150 seconds of speed decrements. The randomization procedure for the time in between every speed variation will ensure that each speed level lasts between 5 and 15 seconds. Each verbal report given by the participants will be immediately recorded by the experimenter.

Obtaining a continuous report of the perceived treadmill speed and confronting it with the actual one will allow us to calculate an intra-subject correlation coefficient between perceived and actual speed, reflecting perceptive correspondence accuracy. This degree of correspondence may vary within a performance and therefore the minute by minute or protocol subphases accuracy dynamics will be also studied (see 'Data and statistical analysis').

[figure not shown]

Figure 9 Perceptive accuracy for imposed speed variations during treadmill walking: Task 1 illustration, wearables placement and Perception vs Performance plot graphic illustration (example pattern of imposed speed).  $\Delta_{min1-6}$  indicates that within-protocol variability in the intrasubject correlation will be studied for the different subphases of the protocol.

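### For participants who reach their speed cap, the treadmill ramp's cap, dwell, phase-length and 0.42 m/s rules cannot all be followed, and the time at the cap is not stated

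*Combined protocol and SAP*

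**What the plan says.** The Part B section on treadmill walking (Task 1) describes a ramp "with fixed increments (of 0,028m/s) but with randomized time in between every acceleration". It allows 15 upward steps, never above the participant's maximal speed. If that speed is reached, "it will stabilize on that value before decreasing toward the baseline speed", and the descent uses as many steps as the ascent. After one minute at comfortable speed, the schedule is "150 seconds of speed increments and 150 seconds of speed decrements", 6 minutes in all. The randomization is to ensure that "each speed level lasts between 5 and 15 seconds". The same section says that a change of 0.42 m/s is imposed on all participants.

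The cap is defined in the section on the range of imposed variations for treadmill walking, from the overground 6MWT: "maximal speed maintained for at least 15 seconds during the test". The Task 1 section restates it as "derived from their overground performance in first minute of 6MWT, see above". Participants "start walking on the treadmill at 50% of their" maximal speed. If that is not comfortable, "the experimenter will adjust the speed based on the" participant's report, with no stated limits. The reserve between comfortable and maximal speed is therefore not fixed by the plan.

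No duration is given for the hold at the cap.

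**The concern.** The schedule is written for a participant who can use all 15 steps. Someone who meets the cap earlier has unused time in a 150 s increment phase. The plan does not say whether the belt stays at the cap until the phase ends, the dwells are stretched, or the phase is shortened. Each choice breaks, or may break, another stated rule.

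Two things are at stake. First, if the belt stays at the cap, the time there grows as reserve shrinks, at a belt-imposed speed that the participant need only have kept for 15 s overground. Second, accuracy is analysed as a within-subject correlation for each protocol subphase (Data and statistical analysis, Part B), with a report every 10 s. Time at the cap replaces reports at changing speeds with reports at one constant speed. If capping differs by group, the mix of belt speeds inside a subphase differs too. That can alter the correlation without any difference in perception.

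**Working it through.** **Inputs.** Task 1 section: step 0.028 m/s, 15 steps, 60 s + 150 s + 150 s, dwell 5-15 s, total change 0.42 m/s. Range section: cap kept for at least 15 s, starting speed 50% of maximum. Not given: participants' maximal speeds, comfortable speed after adjustment, dwell distribution, hold duration.

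**1. The plan's own figures reproduce.** 15 x 0.028 = 0.42 m/s. The mean dwell is 150 / 15 = 10 s, the midpoint of 5-15 s. 60 + 150 + 150 = 360 s = 6 min. With all 15 steps available, the rules agree.

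**2. Total change.** Usable steps: n = the smaller of 15 and the whole number of 0.028 m/s steps in the reserve. A capped participant has n of at most 14, so the change is at most 14 x 0.028 = 0.392 m/s. The 0.42 m/s statement fails for everyone who is capped.

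**3. Dwell limit against phase length.** With one dwell per step, as in the plan's own arithmetic, n dwells last at most 15n s: 150 s at n = 10, 135 s at n = 9, 120 s at n = 8. With n below 10 (reserve below 10 x 0.028 = 0.28 m/s) both rules cannot be met. Counting one extra dwell in the phase shifts this by one step, to n below 9 (reserve below 9 x 0.028 = 0.252 m/s). For n = 10 to 14 both can be met, but only with longer average dwells: 150 / 10 = 15 s at n = 10, 150 / 12 = 12.5 s at n = 12. The descent has the same number of steps and the same 150 s, so the same limits apply.

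**4. If the 150 s phase is kept and dwells average 10 s.** Expected time at the cap in the increment phase is 150 - 10n s. The intervals come from simulating 15 uniform 5-15 s dwells that total 150 s and stopping after n.

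| n | n x 0.028 (m/s) | 150 - 10n (s) | central 95% (s) |
|---|---|---|---|
| 14 | 0.392 | 10 | 5.2-14.7 |
| 12 | 0.336 | 30 | 21.1-38.8 |
| 10 | 0.280 | 50 | 39.4-60.5 |
| 8 | 0.224 | 70 | 58.7-81.0 |
| 5 | 0.140 | 100 | 89.5-110.5 |
| 1 | 0.028 | 140 | 135.3-144.7 |

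The expected hold exceeds 15 s for every n up to 13 (150 - 130 = 20 s). If the first step falls at the start of the phase, or the first dwell of the descent is counted, the range becomes 20-150 s. If spare descent time is also spent at the cap, the hold doubles: 2 x 70 = 140 s at n = 8. The text does not say whether that time belongs at the cap or at baseline.

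**5. If the dwell limit is kept.** The hold is at most 15 s. At 10 s per level the trial lasts 60 + 20n s, which is 220 s at n = 8. Even at 15 s per level it lasts 60 + 2 x 120 = 300 s, not 360 s.

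**6. Who is capped.** If comfortable speed is a fraction f of maximum, the cap binds when maximum is below 0.42 / (1 - f): 0.84 m/s at f = 0.5 (the documented start), and, as assumptions, 1.05 at 0.6, 1.40 at 0.7 and 2.10 at 0.8. The outright conflict in step 3 needs a maximum below 0.28 / (1 - f): 0.56 m/s at f = 0.5 and 0.93 m/s at f = 0.7.

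**7. Reports.** One every 10 s gives about 15 per phase. Of these, about 15 - n come at constant belt speed: about 7 of 15 at n = 8.

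**The case against.** The strongest reply is that a long hold is only one reading. The 5-15 s limit may govern the cap level too, in which case the hold matches the 15 s in the cap's definition. The 150 s lengths also stand in a sentence that points to an example and states 0.42 m/s, so they may describe only the uncapped case. This stands: the documents do not establish that anyone is held for long. But that reading gives up the 150 s phases and the 6-minute total for low-reserve participants, and the plan does not say so.

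A reader might infer that capped participants are held for 30-70 s. That needs n = 8 to 12, for example an assumed maximum of 1.2 m/s with comfortable speed at 70-80% of it, plus 10 s average dwells. Neither speed is in the documents, and at n = 10 or 12 longer dwells can satisfy both timing rules.

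A reader might also infer that the least able people with MS get the longest hold while most controls never meet their cap. No source supports this. Reserve depends on the comfortable speed chosen as well as on ability, and at an assumed 80% the cap would bind below 2.10 m/s in either group.

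On safety, the 15 s is a minimum, and some participants will have kept the speed longer. The plan also has readiness screening, supervised treadmill familiarization with acceleration toward maximal speed, and side bars for brief support. None of these sets a time limit at the cap, but they weigh against describing the gap as a demonstrated hazard.

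**Conclusion.** Wrong as written, for capped participants only. The 0.42 m/s statement fails for all of them. The 150 s phase and the 5-15 s dwell limit cannot both hold below 10 usable steps (reserve below 0.28 m/s), or below 9 if one more dwell is counted. These results follow from the plan's own figures.

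The size of the hold is conditional. Keeping the 150 s phase with 10 s average dwells gives an expected 10-140 s, longer with less reserve. Keeping the dwell limit gives at most 15 s. The plan does not choose between them. It also gives two source windows for the cap, the whole 6MWT and its first minute.

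The number of capped participants and any imbalance between groups cannot be derived. A group bias in subphase accuracy is therefore a possibility to be checked with logged data, not a finding.

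**What to change.** Reconcile the statements in the two treadmill sections on the cap (including its source window in the 6MWT), the dwell limits, the phase lengths and the 0.42 m/s for all participants. The result should be one executable schedule for capped participants, with the time at the cap stated explicitly for both ascent and descent. Which rule gives way is for the sponsor and the clinical team; no particular schedule is proposed here.

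Log the time at the cap and the number of steps for each participant, report both by group, and take them into account when interpreting accuracy by subphase.

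The cost is a short text revision, a matching change to the belt script, and a small addition to the logged data.

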### Task 2: Perceptive accuracy for imposed seat height variations during STS postural transitions

The participants will be tested on a motorized height-adaptable armless chair will allows us to test the perception of imposed sit-to-stand variations in a similar fashion to the treadmill protocol in Part B – Task 1.

A familiarization with the range of seat height, personalized accordingly to the length of the lower leg (see above, 'Range of experimentally-induced performance variations – Sit to stand'), will precede the start of the perceptive task.

Neutral instructions will be provided to the subject before starting the test, by reading the following script: "Start performing STS repetitions at the pace at which you are instructed by the examiner and try, to pay attention, each time, to the seat height. We want you to notice, evaluate and report the seat height to the experimenter relative to the visual scale on the screen: its starting position on the zero value represent your comfortable seat height, the maximum seat height from which I will ask you to stand up. The value of -100, instead, represents the most difficult sit-to-stand you may be asked to perform in the session: the lowest seat-height. Variations may occur at any point throughout the experiment, always within your personalized range. Sometimes it is possible that you will not feel any seat height variation at all. After every STS you will communicate the seat height level you perceived at that point in time, and your report will be recorded".

The seat will be positioned behind the subject at the baseline normalized seat-height (100% lower leg length). Before the start of the experimental perceptive task the participants will be ensured that the chair will always stay safely positioned behind them and that a person is also standing behind in an attentive state to ensure safety.

During the experimental perceptive task the participant will be guided to execute sit-to-stand transitions paced by the experimenter: during the stance phase (10 seconds) in between STS repetitions, the seat height will be modified starting from the baseline (comfortable seat-height= 120% lower leg length) with fixed decrements (of 5% lower leg length) but with randomized n. of repetitions (0, 1 or 2) in between. The seat-height lowering will continue down to the personalized lowest seat-height, stabilizing on that value before increasing toward the baseline height.

Proceeding, from a personalized baseline, with randomized seat height differences and ensuring blinding of participant in a fashion similar to the above presented treadmill task we will be able to obtain an intra-subject correlation coefficient between perceived and actual seat-height level, reflecting perceptive correspondence accuracy. This degree of correspondence may vary within a performance and therefore the minute by minute or protocol subphases accuracy dynamics will be also studied (see 'Data and statistical analysis').

[figure not shown]

Figure 10 Perceptive accuracy for imposed seat height variations during STS postural transitions: Task 2 illustration, wearables placement and Perception vs Performance plot graphic illustration.  $\Delta_{min1-6}$  indicates that within-protocol variability in the intrasubject correlation will be studied for the different subphases of the protocol.

The intensity of perceived fatigue and a short structured interview will follow in the same way as in task 1 (Treadmill walking).

---

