#### **Range of imposed performance variations (part B) – Sit to stand**

A STS seat height range definition procedure will permit the quantification of the appropriate personalized range of experimentally-induced performance variations for every participant. The 30CST requires the maximal frequency of STS transitions to be produced by the subjects on a standardized chair (fixed seat height of 43.2 cm), exposing them to incremental challenges due to physical exertion over a short time. In our study the baseline seat height will be normalized on the physical characteristic of the participants (=100% of the distance from the ground to the inferior margin of the patellar bone, measured in sitting, including the height of the shoes sole, wearing the same shoes as in all the other experimental parts and after ensuring vertical alignment of the tibia). The STS seat height range that will be used as personalized range of experimentally-imposed

performance variations (in Part B) will be then calculated as: baseline seat height  $\pm$  20% (from comfortable to lowest seat height, see 'verbal descriptors' below).

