#### **Familiarization with perceptive task for Part B – 'Perception of imposed performance variations'**

At this point the experimenter will present two vertical visual scale on a screen, ranging from 0 to +100 or from 0 to -100, which have been designed to match the participants' perception of ongoing motor performance, either for treadmill walking or STS.

Verbal descriptors will be positioned on the right side of the scale at every 10th step describing different levels of walking speed or STS difficulty level. Note (see below) that the verbal descriptors of the two visual scales will be inversely directed, but that 'minimal seat height' represent the most difficult condition in the STS task and therefore correctly occupies the upper limit of the scale.

Perceived treadmill speed scale 0% =your comfortable speed; +100% =your maximal speed

Perceived seat-height scale 0% =your comfortable seat height; -100% = your minimal seat height

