### **Hypothesis**

- PwMS and HC will differ in the measured outcomes of perceptive accuracy for imposed walking speed variations during treadmill-based experimental protocols, lower accuracy is expected in PwMS with higher reported fatigue
- PwMS and HC will differ in the measured outcomes of perceptive accuracy for imposed STS vertical excursion variations during self-paced experimental protocols, lower accuracy is expected in PwMS with higher reported fatigue
- PwMS will be less accurate than controls to a larger extend in the last subphase of the protocol (i.e. returning to comfortable speed or seat height levels from the most difficult performance level)
- Lower correspondence between measured and subjective (i.e. confidence rating) dimensions of perceptive accuracy is expected in PwMS

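### Part B does not state its imposed stimulus consistently (seat baseline, treadmill range, maximal speed), and the planned phase-wise correlation is undefined in the constant-speed first minute

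*Combined protocol and SAP*

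**What the plan says.** **Seat.** Under Range of imposed performance variations (part B) – Sit to stand, "the baseline seat height will be normalized on the physical characteristic of the participants (=100% of the distance from the ground" to the lower edge of the patella), and the range is that baseline ± 20%, described as running "from comfortable to lowest seat height". The report scale is "Perceived seat-height scale 0% =your comfortable seat height; -100% = your minimal seat height". In Part B, Task 2, the set-up sentence reads "The seat will be positioned behind the subject at the baseline normalized seat-height (100% lower leg length"). The task sentence in the same section reads "starting from the baseline (comfortable seat-height= 120% lower leg length) with fixed decrements (of 5% lower leg length"), and the sequence ends by "stabilizing on that value before increasing toward the baseline height". The participant script says that scale zero is the starting position, the comfortable height and the highest seat that will be used.

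**Treadmill.** Part B, Task 1 uses 15 steps of 0.028 m/s, never above the participant's maximal speed, stabilising there before the same number of steps down. It adds that "this protocol will last 6 minutes and will impose the absolute magnitude of speed changes (0,42 m/s) for all participants". The phases are 60 s of constant comfortable speed, 150 s up and 150 s down, with each level lasting 5 to 15 s.

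**Maximal speed.** The treadmill range section takes the best speed held for at least 15 s during the 6MWT. Part B, Task 1 takes it from the first minute of the 6MWT and refers back, but no first-minute rule appears earlier.

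**Analysis.** Data and statistical analysis computes within-subject correlations separately by phase, applies Fisher z, and enters them in a mixed ANOVA with subphase and group. Task 1 also plans minute-by-minute accuracy. One Part B hypothesis concerns the last subphase, "returning to comfortable speed or seat height levels from the most difficult performance level".

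**The concern.** The Part B outcome is a correlation between imposed and reported level. Such a correlation depends on the range of levels imposed and the time spent at each, as well as on perception. A stimulus that can be run in more than one way from the same text, or that differs in range between participants, can therefore move the outcome with no difference in perceptive accuracy. Walking capacity decides who reaches the cap, and it may differ between PwMS and controls, so the treadmill wording matters more than the seat wording. Separately, a phase in which the imposed level never changes cannot yield a correlation at all, yet the plan treats the phases as levels of the time factor.

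**Working it through.** **1. Seat.** Inputs: baseline 100% or 120% of lower leg length, range 100% ± 20% = 80% to 120%, step 5%.
- Start at 120%: (120 − 80)/5 = 8 steps down, starting at scale value 0.
- Start at 100%: (100 − 80)/5 = 4 steps down, starting at (100 − 120)/40 × 100 = −50.

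The script, the scale, the stated direction of the range and the task sentence all put start and zero at the comfortable (top) height. The 100% set-up sentence is the one that does not fit. The return height is called only the baseline, so it inherits the ambiguity.

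**2. Treadmill range.** The plan's own figures reproduce: 15 × 0.028 = 0.42 m/s; 60 + 150 + 150 = 360 s; 150/15 = 10 s per level on average, inside 5–15 s.

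The cap binds when maximal speed × (1 − comfortable/maximal) < 0.42.
- Ratio 50% (the protocol's starting value, adjusted afterwards to the participant's report): 0.42/0.5 = 0.84 m/s.
- Ratio 70% (assumed): 0.42/0.3 = 1.40 m/s.
- Examples at 70%: maximal 1.2 m/s leaves 0.36 m/s, so 12 steps (0.336 m/s); maximal 1.0 m/s leaves 0.30 m/s, so 10 steps (0.28 m/s).

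**3. Timing of a capped run.** The text gives a hold but no length. Take levels of 10 s on average and k steps, with the first increment at 60 s.
- Decrements timed to end at 360 s: hold = 300 − 20k + 10, which is 70 s (k = 12) or 110 s (k = 10). The hold then runs into the decrement phase.
- Decrements starting at 210 s, as the phase lengths imply: hold = 150 − 10(k − 1), which is 40 s or 60 s. The run then returns to comfortable speed before 360 s.

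Either way the hold exceeds 15 s, and the text does not choose between the two.

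**4. Maximal speed.** The definitions agree only if the best 15 s falls in the first minute. Suppose the first-minute value is lower by a fraction d (assumed) and sets the cap, while comfortable speed is 50% of the whole-test maximum. The threshold becomes 0.42/(1 − d − 0.5): 0.93 m/s at d = 5% and 1.05 m/s at d = 10%.

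**5. Constant phase.** r = cov(x, y)/(SDx × SDy). In the first 60 s SDx = 0, so r is 0/0 for every participant, capped or not. Fisher z cannot repair that. With three phases as the time factor, the first level is empty.

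**6. Effect of a cap on r.** Simulation: one report per 10 s for 360 s, Gaussian noise added to actual speed (SD 0.10 m/s, assumed), levels 5–15 s, return phase = reports after 210 s, 4,000 runs, back-transformed mean Fisher z.

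| Steps | Decrements end at 360 s | Decrements start at 210 s |
|---|---|---|
| 15 (uncapped) | 0.80 | 0.80 |
| 12, with hold | 0.785 | 0.75 |
| 10, with hold | 0.74 | 0.68 |

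Minute 4 has constant imposed speed in about 49% (12 steps) and 99% (10 steps) of runs in the first column, and in 0% in the second.

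With noise constant in scale points instead (SD 15 points, comfortable 70% of maximal, both assumed), r is 0.905 uncapped and 0.92–0.93 capped when decrements end at 360 s. Starting them at 210 s removes that small gain without a material loss.

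**The case against.** Much can be said for the plan. The seat task can be worked out from the script, the scale and the task sentence, and the 100% sentence may describe only a reference or parking height. A reader might infer that participants would start halfway down the scale with four steps. The documents do not support that, because the script rules it out, and an error applied to everyone would affect both groups alike. What stands is that one word carries two values and also names the return point.

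On the treadmill, the sentence on the cap can be read as a rule with its exception, with the phrase about all participants meaning an absolute rather than a relative step. The 5–15 s rule may cover only the intervals between changes, since the first minute already lies outside it. This is fair, but the timing of the hold is still unstated. Stretching the levels to fill 150 s is not in the text, which speaks of stabilising, so I give it no weight.

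A reader might also infer that the cap biases the comparison of PwMS with controls. The documents give no speeds, reports are made on a personal 0–100 scale, and with noise in those units the loss disappears. Nor does the cap by itself make minute 4 undefined: that depends on when decrements start. The certain gap is minute 1, and it has nothing to do with the cap.

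Finally, the reference back in Part B, Task 1 may intend the 15-second definition. It does not say so.

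**Conclusion.** The concern holds as a set of internal contradictions plus one undefined quantity. The seat baseline has two values 20% of lower leg length apart. The 0.42 m/s change cannot apply to everyone under the plan's own cap. Maximal speed, which sets both the cap and the +100 anchor, has two definitions. The phase-wise or minute-wise r does not exist in the first treadmill minute for anyone.

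The effect of a cap on r ranges from nothing material (noise in scale points) to a fall from 0.80 to 0.68 (10 steps, noise SD 0.10 m/s, decrements from 210 s). Even a 12-step cap can cost between 0.015 and 0.05, depending on timing. The noise SDs, the 70% ratio, the 5–10% gap and the hold timing are assumptions. The share of capped participants, and so any group bias, is not known from the documents. Minor to should-fix, in a study that calls itself exploratory.

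**What to change.** - **Seat:** reconcile the range section, the scale and Part B, Task 2 so that one named height is the start, the return and scale zero. The sponsor decides which passage governs.
- **Maximal speed:** reconcile the treadmill range section with Part B, Task 1 to one definition. Again the sponsor decides.
- **Treadmill range:** restate 0.42 m/s as the maximum change, subject to the cap. State how long a capped run holds, when its decrements start, and how this fits the 150 s phases and the 5–15 s rule.
- **Analysis:** leave the constant-speed phase out of the correlation and the subphase factor, or use an index that is defined there, such as absolute error. Apply the same rule to any other segment with constant imposed speed.
- **Records:** keep each participant's number of steps and cap status. Optionally repeat the Part B group comparison without capped participants.

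The cost is wording, a change to the treadmill control file and at most one extra analysis, with no added visits or participants. If data already exist, steps and cap status can be read from the recorded speeds. The optional analysis has a downside: a smaller n, and a result that describes faster walkers only.

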## Task 2: Perceptive accuracy for STS duration variations during repeated STS postural transitions

The participants will be tested on a armless chair of normalized seat height, for their ability to accurately perceive changes in their self-paced sit to stand duration.

They will be instructed to perform STS repetitions at a fixed pace, but to execute each transition from sitting to standing as fast as possible. Sitting with the back rested on the back-support will be the starting position of the test. After the first STS transition (i.e. starting from the first standing position), they will be presented with a countdown of 10 seconds during which they must return to the sitting position and, from that position, perform the following STS transition. The participant will be asked to use the time in between STS repetitions to evaluate their sit-to-stand duration, comparing it with the previous, and decide if to report (or not) a change in STS duration (using the same handheld sensor as during the 6MWT). The STS execution will be stopped by the examiner after 36 repetitions.

Neutral instructions will be provided to the subject before starting the STS test by reading the following script: "When you will hear the beep tone, squeeze the sensor and start performing sit-to-stand repetitions, doing each of them standing up at the maximal speed that you can use to stand up safely. Be aware that we are not asking you to perform as many repetitions you can in a limited amount of time, but that you will be asked to stand up from the chair once every 10 seconds, you just have to do each repetition at your maximal speed: going from sitting to standing as fast as you can. Natural variations in your sit-to-stand speed may occur between repetitions. We want you to notice and, starting from the second repetition, report them using the handheld sensor: if you perceived a change in the time needed to stand up, being it shorter or longer does not matter (you will not have to indicate it), squeeze the sensor in your hand during the resting phase. In between repetitions you will have 10 seconds to decide if to report a change: in the case you didn't notice any change, simply don't squeeze."

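### The seat-height task has no stated length or phase totals, and its random repetition rule does not fix the number of reports in the lowering and rising limbs

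*Combined protocol and SAP*

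**What the plan says.** The combined protocol and SAP describes four experimental tasks. Three have a stated length:

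- Part A, Task 1 is a six-minute walk.
- Part A, Task 2 has one stand every 10 seconds: "The STS execution will be stopped by the examiner after 36 repetitions".
- Part B, Task 1 (treadmill) lasts 6 minutes: one minute at stable speed, then "150 seconds of speed increments and 150 seconds of speed decrements". Each speed level lasts a random 5 to 15 seconds.

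Part B, Task 2 (seat height) gives a path and a dwell rule only. The seat moves "with fixed decrements (of 5% lower leg length) but with randomized n. of repetitions (0, 1 or 2) in between". The course is then: "The seat-height lowering will continue down to the personalized lowest seat-height, stabilizing on that value before increasing toward the baseline height". The length of the hold at the bottom is not given. Participants report once after every stand, so reports equal repetitions.

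The same section states two starting heights: the seat is placed at "baseline normalized seat-height (100% lower leg length", and two sentences later the baseline is given as "comfortable seat-height= 120% lower leg length". The familiarization section on the sit-to-stand range sets baseline plus or minus 20%, described as "from comfortable to lowest seat height, see 'verbal descriptors' below".

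For analysis, the task section says that "minute by minute or protocol subphases accuracy dynamics will be also studied". The section Data and statistical analysis puts Fisher-z transformed within-subject correlations into a mixed ANOVA with protocol subphase and group as factors. A Part B hypothesis expects the larger deficit in people with MS in the last subphase, the return to the comfortable level.

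**The concern.** Each participant's data point for a limb is one correlation, and its precision depends on how many reports that limb contains. If the count is random, participants enter the ANOVA with equal weight but unequal precision, and a few may have too few reports for a correlation at all. The return limb, which carries its own hypothesis, is as exposed as the lowering limb. A clock-minute index would add a further problem: the same minute could fall in different limbs for different participants.

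The treadmill task avoids this by fixing the length of each phase while leaving the dwell at each level random. The seat-height task is meant to resemble it but states no such limit.

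**Working it through.** **Comparators, from the plan's own figures.** Treadmill: 60 + 150 + 150 = 360 s = 6 min. Fifteen levels of 5 to 15 s could take anything from 15 × 5 = 75 s to 15 × 15 = 225 s; fixing the phase at 150 s (15 × 10 s) removes that spread. Part A sit-to-stand: 36 × 10 s = 6 min. The seat-height task states no figure to reproduce.

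**Inputs for the seat-height task.** Step 5%; counts 0, 1 or 2; lowest height 80% of lower leg length (100% minus 20%). Steps per limb: (120 − 80)/5 = 8 from the higher starting height, (100 − 80)/5 = 4 from the lower.

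**Assumptions not in the documents.** The three counts are equally likely; draws are independent and made anew for each participant; a repetition cycle lasts 10 s; no extra repetitions occur during the hold at the bottom.

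One draw has mean 1 and variance 2/3. For k draws the mean is k and the SD is √(2k/3).

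**Reading 1: 0 to 2 extra repetitions at a height (8 steps per limb).**
- Total = 17 obligatory stands (8 down + 8 up + 1) + 16 draws. Mean 33; SD √(32/3) = 3.27.
- The exact 95% range of 16 draws is 10 to 22, so the total is 27 to 39 (limits 17 to 49). At 10 s each that is 4.5 to 6.5 min.
- Per limb: 8 + 8 draws, mean 16, SD √(16/3) = 2.31, 95% range 12 to 20.
- Fisher-z standard error 1/√(n − 3): 0.333 at n = 12, 0.277 at 16, 0.243 at 20.
- Averaged over the draws, 1/(n − 3) is 0.0796, against 1/13 = 0.0769 with 16 fixed. In standard-error terms, √0.0796 = 0.282 against 0.277: under 2%.

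**Reading 2: 0 to 2 repetitions in all per step (8 steps per limb).**
- Reports per limb: mean 8, SD 2.31, 95% range 4 to 12.
- There are 3⁸ = 6561 equally likely sequences. Those with 0, 1, 2 or 3 reports number 1 + 8 + 36 + 112 = 157, and 157/6561 = 2.4%. Adding the 266 with exactly 4 gives 423/6561 = 6.4%.
- Over 88 participants and two limbs: 176 × 0.0239 ≈ 4 limbs with 3 or fewer reports, where 1/√(n − 3) is undefined.
- Standard error: 1.0 at n = 4, 0.447 at 8, 0.333 at 12.
- Among limbs with at least 4 reports, the average of 1/(n − 3) is 0.257, against 1/5 = 0.200 with 8 fixed: √0.257 = 0.507 against 0.447, so fixing the count lowers it by about 12%.
- One third of heights would be passed with no stand.

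A simulation with an assumed level of report noise agrees. Fixing the counts changed the SD of the per-limb Fisher-z by about 1% under reading 1 and cut it by about 15% under reading 2 (roughly 0.48 to 0.40, both rounded). The noise level is an assumption, so this is indicative only.

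**Effect of the lower starting height.** With 4 steps per limb under reading 2, (1 + 4 + 10 + 16)/3⁴ = 31/81 = 38% of limbs have 3 or fewer reports. Under reading 1 the limb mean is 4 + 4 = 8, with a minimum of 4.

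**The case against.** Much of the case rests on silence. The plan says the task follows the treadmill protocol, and the Figure 10 caption carries the same minutes 1 to 6 label, so about 6 minutes was probably intended. The reading 1 mean of 33 repetitions (5.5 min) fits that. The figure itself is not available. A single sequence shared by everyone would remove the variation between participants, and the plan does not rule that out. The study is exploratory, and the ANOVA already uses protocol subphase as its time factor. All of this stands and limits the size of the point. It does not remove it: nothing says how the random counts fit 6 minutes. If the run were cut at 36 repetitions, about 14% of reading 1 sequences would not complete the return limb.

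A reader might infer stronger versions that the documents do not support:

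- **That the heights follow a random walk.** The path is a fixed staircase down and up; only the dwell at each height is random.
- **That participants make differing numbers of maximal-effort stands, so that fatigue change reflects the draw.** The maximal-speed instruction belongs to Part A. Here the examiner sets the pace, and no effect of a few stands on the fatigue score is shown.
- **That the task ends when the path is complete, so some participants lack a sixth minute.** No stopping rule is stated either way.
- **That the group comparison is biased.** The draw does not depend on group.

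**Conclusion.** The point holds as a gap in the design of one task. The seat-height task alone has no stated length or phase totals, and its repetition rule as written does not fix the number of reports per limb. The consequence is noise and unequal precision in the group by subphase ANOVA and in the test of the return-limb hypothesis.

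The size turns on what zero means. If it means no extra repetition, every height is reported at least once and the loss is small. If it means no repetition at all, the loss is material, and a few limbs yield no usable correlation. The lower starting height makes that second case much worse. These sizes depend on the assumptions of equal probabilities, independence and a new sequence for each participant. This is an inexpensive improvement, not a threat to the study's validity.

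**What to change.** 1. Reconcile the two starting heights first, since they determine whether a limb has 8 steps or 4.
2. State whether zero means no extra repetition or no stand at that height.
3. For each participant, draw a random permutation of one fixed set of repetition counts within each limb. Order and dwell stay random, while every participant has the same number of reports in the lowering limb, in the rising limb and in total, as the fixed treadmill phases already ensure for time. This is compatible with the present rule: under reading 1, 1107 of the 6561 possible sequences for an 8-step limb (17%) already sum to 16.
4. State the resulting total and the length of the hold at the lowest height.
5. For this task, define within-task change by limb (protocol subphase) and drop the clock-minute option.

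The cost is a change to how the sequence is generated before the next participant, plus a few sentences in the plan; no visit time or staff are added. The downside is a slightly more predictable sequence, which matters little because participants do not know the set of counts.
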